7.2.2. Procedures Performed at the Safety Visit – on site

The following procedures/ assessments will be performed:

- ✓ Study personnel will review the memory aid information with subjects and assess and record all solicited events / unsolicited reactions, AEs, SAEs and concomitant medications on the appropriate data collection form;
- ✓ Vital signs (as applicable), including body temperature and pulse, will be obtained prior to the first study vaccination. Subjects must not eat or drink anything hot or cold, or smoke within 10 minutes prior to taking body temperature;
- ✓ A targeted physical examination and/or vital signs collection may be performed by a study clinician if assessed as needed based on review of recent medical history;
- ✓ Counsel women of childbearing potential on contraception and avoidance of pregnancy.
- ✓ Study personnel will review interim medical history (other than reactogenicity events) with subjects and assess and record all unsolicited AE/SAEs and concomitant medications on the appropriate data collection form.

7.2.3. Procedures Performed at the Safety Visit – phone call

The following procedures/ assessments will be performed:

- ✓ Call subject on days 3, 7, 14, 24, 28, 42, 81, 141, 171, 231, 261, 351 and verbally confirm compliance with daily completion with study dairy (till Visit 5).
- ✓ Review any changes in the subject's concomitant medications and treatment information;
- ✓ Assess need for contraception and adherence to applicable lifestyle requirements. Establish willingness and ability to comply with lifestyle requirements going forward in the study;
- ✓ Assess and record any Adverse Events since the last visit.

7.2.4. Procedures Performed at the Second Vaccination Visit

- ✓ Study personnel will review the memory aid information with subjects and assess and record all solicited, reported reactions, AEs, SAEs (as applicable) and concomitant medications on the appropriate data collection form.
- ✓ Counsel women of childbearing potential on contraception and avoidance of pregnancy.
- ✓ Vital signs, including oral temperature and pulse, will be obtained prior to the first study vaccination. Subjects must not eat or drink anything hot or cold, or smoke within 10 minutes prior to taking oral temperature.
- ✓ A targeted physical examination should be performed by a study physician if assessed as needed based on medical interview concerning period between Visit 1 and Visit 5.
- ✓ Examine the vaccination site for Dose 1.
- ✓ Eligibility criteria will be reviewed with subjects prior to the second study vaccination to assure continued eligibility.
- ✓ Obtain interim medical history by interview of subjects prior to the second study vaccination and note any changes since the previous visit.
- ✓ All concomitant medications will be recorded on the appropriate data collection form prior to the second study vaccination.
- ✓ All unsolicited AEs/ SAEs will be assessed and recorded on the appropriate data collection form prior to the second study vaccination.
- ✓ A urine pregnancy test will be performed within 24 hours prior to the second study vaccination on all female subjects of childbearing potential. Results must be negative and known prior to the second study vaccination;
- ✓ Pre-administration reactogenicity assessments will be performed prior to the first study vaccination to establish baseline. Subjects will then receive a single dose of study vaccine via IM injection in the deltoid muscle of the non-dominant arm. The site of injection (right or left arm) and time of administration will be recorded on the appropriate data collection form. Subjects will be observed in the clinic for at least 30 minutes after the first study vaccination. The study vaccination site will be examined, and observed reactions, AEs, SAEs (as applicable) will be assessed and recorded on the appropriate data collection form prior to discharge from the clinic.
- ✓ Subjects will be provided with a memory aid (paper diaries) and other study-related materials to record daily temperature, solicited injection site and systemic reactions, any unsolicited AEs, and concomitant medications. Subjects will be encouraged to take their temperature on the vaccination day in the evening and then at selected approximately the same time each day for next 21/28 days after the vaccination day. Subjects will be instructed on how to complete the diary, prior to discharge from the clinic. Subjects will be instructed to notify the study center if they develop any reactions after the first study vaccination. PI or appropriate SI will assess the

reaction and will give the subject further instructions on the proper course of action, including request for return to the clinic for immediate evaluation. The subjects will be instructed to return the completed diary, covering period between Visit 1 and Visit 2.

7.3. Unscheduled Visits

All attempts should be made to keep patients on the study schedule.

Unscheduled visits may occur at any time during the study. Any of the following activities may be performed:

- ✓ Review memory aid (till Visit 10)
- ✓ Review and record all concomitant medications (if within 22 days after the last study vaccination day, inclusive of the vaccination day).
- ✓ All reactions recorded in diary/-ies, AEs, SAEs will be recorded on the appropriate data collection form. Recording of AEs in the EDC will be limited to SAEs if after 21 days after the last study vaccination day.
- ✓ Obtain interim medical history by interview of subjects and note any changes since the previous visit (if indicated).
- ✓ If deemed as relevant and/or needed, perform physical examination and/or obtain vital signs including oral temperature. Subjects must not eat or drink anything hot or cold, or smoke within 10 minutes prior to taking oral temperature.
- ✓ Examine study vaccination site and perform post- administration reactogenicity assessment (if within 14 days after the last study vaccination, inclusive of vaccination day)

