	
The 4-fold increase rate, GMT and GMI of anti-SARS-CoV-2 neutralizing antibody in 28 days after 2 doses of immunization.
 
The GMT of anti-SARS-CoV-2 neutralizing antibody in 3rd month, 6th month, 9th month, and 12th month after 2 doses of immunization.
 
Safety endpoints
 
 • The incidence of any adverse reactions/events within 30 minutes after each dose of vaccine • The incidence of solicited adverse reactions/events within D0~7 and unsolicited adverse reactions/events within D8~21 days after first dose of vaccination. The incidence of solicited adverse reactions/events within D0 ~ 7 and unsolicited adverse reactions/events within D8~28 days after second dose of vaccination. • The incidence of serious adverse events (SAE) from the beginning of the first dose to 12 months after the whole course of immunization.

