4.4.3. Safety Endpoint

The incidence of adverse reactions/events within 30 minutes after each dose of vaccination.

The incidence of solicited and unsolicited adverse reactions/events within D0 ~ 7, and unsolicited events and SAEs within D8 ~ 21/28 after each dose of vaccination.

The incidence of serious adverse events (SAE) from the first dose of vaccination to 12 months after the last dose of vaccination.

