The same statistical methods as above are used to evaluate VEs against severe cases of COVID-19 and deaths accompanied by COVID-19.

(4) Immunogenicity analysis (FAS and PPS analysis):

Statistical description: The antibody titer should be logarithmically transformed. Minimum value, maximum value, median and quartile spacing, GMT and 95% CI should be shown.

Comparison of antibody levels before immunization: Logarithmic conversion was carried out on antibody titers, and two independent sample T tests (normal and homogeneous variance) or corrected T tests (normal but uneven variance) shall be used to compare the GMT of neutralizing antibodies against COVID-19 before immunization between the experimental and placebo groups with various ages.

Comparison of antibody levels after immunization:

- ✓ calculate the antibody 4-fold increase rate and 95% CI of anti-SARS-CoV-2 antibody in the experimental and placebo groups with various ages after immunization, and make superiority comparison. If the lower limit of 95% CI of antibody 4-fold increase rate is $\geq 10\%$, the superiority hypothesis is valid;
- ✓ calculate 95% CI of GMT ratio of anti-SARS-CoV-2 antibody in the experimental and placebo group after immunization. If the lower limit of 95% CI ratio is ≥ 1.1 , the superiority hypothesis is valid;
- ✓ calculate the GMI and 95% CI of anti-SARS-CoV-2 antibody in the experimental group after immunization.

(5) Safety analysis (SS analysis)

Describe the frequency and number and incidence of adverse reactions/events. If a subject manifest the same adverse reaction/events repeatedly, the description on this adverse reactions/events should indicate the most severity, the closest relationship with vaccination and the earliest starting time. However, in the list of adverse reactions/events, all adverse reactions/events will be listed.

Using χ^2 test or correct χ^2 test or Fishers exact test, the incidence of total adverse reactions, systemic adverse reactions, local adverse reactions and unexpected adverse reactions in the experimental and placebo groups within 30 minutes, 0-7 days and 8-28 days after inoculation of each dose were compared χ^2 test or correct χ^2 test or Fishers exact is used to compare the difference of SAE incidence rate between the experimental and placebo groups within 360 days after the whole inoculation. The rank sum of two independent samples is used to compare the average grade of adverse reactions in the experimental and placebo groups.

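### The AE windows conflict: at unscheduled visits non-serious AEs stop being entered 21 days after the last dose although the dose-2 endpoint runs to day 28, and the dose-1 analysis window of days 8-28 runs past its own endpoint into the dose-2 reaction period

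*Protocol*

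**What the plan says.** **Endpoints.** The safety endpoints in the Synopsis give each dose its own window for unsolicited events: "unsolicited adverse reactions/events within D8~21 days after first dose of vaccination" and "unsolicited adverse reactions/events within D8~28 days after second dose of vaccination". Section 4.4.3 uses a shorter form, "unsolicited events and SAEs within D8 ~ 21/28 after each dose of vaccination", and section 4.7.1 uses the same 21/28 notation for collection.

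**Recording.** Section 7.3 opens with "Unscheduled visits may occur at any time during the study. Any of the following activities may be performed", and its list includes "Recording of AEs in the EDC will be limited to SAEs if after 21 days after the last study vaccination day". In the same list, concomitant medication is recorded for 22 days counting the vaccination day, and memory-aid review continues to Visit 10. Table 4 ticks adverse events at every visit, including D42 and D49, and the diary card at Visit 10 (D49).

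**Analysis.** Section 9.3(5) compares adverse reactions "within 30 minutes, 0-7 days and 8-28 days after inoculation of each dose were compared". The Synopsis has the same text.

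**Dosing interval.** Section 6.6 places the two doses at D0 and D21 (+7 days).

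**The concern.** There are two separate mismatches.

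(a) The recording rule in section 7.3 ends before the dose-2 endpoint does. A subject who comes in with a new non-serious complaint in the fourth week after dose 2 falls inside the endpoint window but outside the stated rule for EDC entry. An analysis window can be corrected later. An event that was never entered cannot be recovered from the database.

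(b) The analysis applies days 8-28 to both doses. For dose 1 that goes beyond the endpoint and reaches past the second injection. The compared outcomes are total, systemic, local and unexpected reactions, so an injection-site reaction on the day after dose 2 can meet the definition of a late dose-1 event and of an early dose-2 event.

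At stake are the completeness of the late dose-2 row and the attribution of events in the late dose-1 row. If the text is followed as written, those rows do not estimate the endpoints that the protocol states.

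**Working it through.** The plan gives no figure to reproduce. The check is a count of days on the stated windows, with both end days included.

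**Inputs**
- Dose-1 endpoint, unsolicited events: days 8-21 (Synopsis).
- Dose-2 endpoint, unsolicited events: days 8-28 (Synopsis).
- Analysis window after each dose: days 0-7 and 8-28 (Synopsis; section 9.3(5)).
- EDC entry of non-serious AEs at unscheduled visits: to day 21 after the last dose (section 7.3).
- Dose 2 on study day d, with d from 21 to 28 (section 6.6).

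**(a) Dose-2 endpoint days beyond the cut-off**
- Length of the endpoint window: 28 - 8 + 1 = 21 days.
- Days after the cut-off: 28 - 22 + 1 = 7 days (days 22-28).
- Share: 7/21 = 33% of the window.
- With dose 2 on D21 these are study days 21 + 22 = 43 to 21 + 28 = 49.

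The concomitant-medication limit in the same list, 22 days counting the vaccination day, covers days 0-21. It makes the same cut, so day 21 does not look like a single misprint. The list also conflicts with itself: the diary is still reviewed to Visit 10, which is D49, or 28 days after a dose 2 given on D21.

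**(b) Dose-1 analysis window against the dose-2 reaction period**
- The dose-1 analysis window ends 28 - 21 = 7 days after its endpoint window.
- The dose-2 day 0-7 period covers study days d to d + 7. For d from 21 to 28, d + 7 is at least 28, so its overlap with study days 8-28 runs from d to 28. Overlap = 28 - d + 1 = 29 - d days.

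| Dose 2 on | Overlap (days) | Share of the 21-day dose-1 window |
|---|---|---|
| D21 | 29 - 21 = 8 | 8/21 = 38% |
| D24 | 29 - 24 = 5 | 5/21 = 24% |
| D28 | 29 - 28 = 1 | 1/21 = 5% |

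Every permitted dose-2 date gives some overlap. On the nominal schedule, D21, it covers the whole dose-2 day 0-7 period. The endpoint's own window of days 8-21 meets the dose-2 period only on D21 itself, and only when dose 2 is given that day.

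**Can the wording be reconciled as it stands?** The 21/28 notation in sections 4.4.3 and 4.7.1 can be read as 21 days after dose 1 and 28 after dose 2, which agrees with the Synopsis endpoints. The analysis text cannot be read that way, because it gives one window, 8-28, and applies it to each dose.

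**The case against.** **On recording.** The day-21 sentence sits in a list of optional activities at unscheduled visits. Scheduled collection continues: Table 4 has AEs at D42 and D49, the diary runs for 21/28 days and records unsolicited events (section 7.2.4), and completed dose-2 diaries are returned to the site (section 7.4.6). A reader might infer that all EDC entry of non-serious AEs stops at day 21, or that late dose-2 events are shown to be under-recorded. The documents support neither. The exposed events are non-serious ones seen at an unscheduled visit on days 22-28 and then not picked up from the diary or at Visit 10. The 33% is a share of calendar days, not of events. SAEs are not affected. The contradiction remains, because Table 4 is one more place with which section 7.3 disagrees.

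**On analysis.** Collection is split by dose: section 7.2.4 has AEs recorded before the second injection and provides a diary at that visit. The rule for attributing an event to a dose may stand in the SAP, which is not at hand, so double counting is the literal reading and not an established outcome. That stands. But the window itself is stated in the protocol and disagrees with the protocol's own endpoint, so this is not a detail left for later.

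**On direction.** A reader might infer that dose-1 reactogenicity in the vaccine arms is overstated. Section 7.4.4 defines reactogenicity through day 7, and the dose-1 day 0-7 comparison is untouched. Only the late dose-1 row is exposed. The rule is the same in all arms, and placebo recipients also receive a second adjuvant injection (section 4.3), so no built-in advantage for one arm follows.

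**Conclusion.** The inconsistency is real and limited in reach. At unscheduled visits, the section 7.3 rule leaves non-serious events on 7 of the 21 days of the dose-2 unsolicited window at risk of not being entered. The dose-1 analysis window exceeds its endpoint by 7 days and overlaps the dose-2 day 0-7 period by 1 to 8 days, depending on the date of dose 2.

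This rests on taking the stated windows literally, on dose 2 being given within D21-D28, and on no attribution rule elsewhere overriding the analysis text. How many events are affected cannot be derived from the protocol. The consequence is for the completeness and per-dose attribution of non-serious events. The mismatch does not touch the primary efficacy analysis, its type I error or SAE reporting. The correction is worth making because it is cheap and because unentered events cannot be restored afterwards.

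**What to change.** - **Section 7.3:** extend the EDC cut-off for non-serious AEs from 21 to 28 days after the last dose, and align the 22-day concomitant-medication limit with it.
- **Synopsis and section 9.3(5):** replace the single 8-28 day window after each dose with the endpoint windows. For dose 1 use days 8-21, ending at dose 2 if that comes earlier or on the same day. For dose 2 use days 8-28. Keep days 0-7 after each dose unchanged.
- **Attribution:** count any AE with onset after dose 2 under dose 2 only.
- **Decision on the gap:** when dose 2 is given after D22, events from D22 up to dose 2 fall in neither per-dose endpoint window. If they are to be tabulated under dose 1, closing the analysis window at dose 2 is not enough: the dose-1 endpoint in the Synopsis and the matching text in sections 4.4.3 and 4.7.1 must be amended as well. Otherwise a new mismatch between endpoint and analysis replaces the present one.

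The cost is wording, an adjustment to the EDC cut-off and a few more AE entries.

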7.4. Study Procedures

7.4.1. Vital signs

Vital signs (sitting blood pressure, pulse rate, respiratory rate and temperature) will be measured after 5 minutes of rest as indicated in the Table 4. Schedule of Events.

Blood pressure and heart rate will be measured using a standard calibrated blood pressure measuring device. A BP device that uses multiple cuff sizes based on the arm circumference is the required type of device. The appropriate cuff size for the subject must be used to ensure accurate measurement. The same device should be used throughout the study. Subject should be seated in a chair, back supported, and arms bared (free of restrictions such as rolled-up sleeves, etc.) and supported at heart level. Measurements should be taken on the same arm at each visit (preferably non-dominant).

Note: in case of high blood pressure values at screening, the investigator is responsible for the optimization of the patient's treatment to achieve blood pressure targets as defined by local

guidelines or the Seventh Report of the Joint National Committee on Prevention, Detection, Evaluation, and Treatment of High Blood Pressure (Chobanian 2003).

Heart rate should be measured at approximately the same time as BP for a minimum of 30 seconds. When the timing of BP and pulse (heart) rate measurements coincides with a blood collection or other study procedure, BP and pulse (heart) rate should be obtained first.

Measurement of body temperature will be collecting using the tympanic methods and the same method should be used consistently throughout the study.

7.4.2. Physical Examination

Standard physical examination should be performed prior to the first study vaccination, but if subject's medical history is known based on medical records, a limited, targeted physical examination may be performed instead of standard scope PE prior to the first study vaccination by a study clinician, however in any case neurologic component of PE and physical examination of head/upper respiratory tract must be performed. On visits other than 1 limited, targeted physical examination may be performed if assessed by investigator as needed.

Additional physical exams will be performed at other time points according to Table 4. Schedule of Events. Care should be taken to examine and assess any abnormalities that may be present, as indicated by the patient's medical history.

7.4.3. Body Weight and Height

Body weight should be obtained at time points according to Table 4. Schedule of Events, with the patient wearing undergarments or very light clothing and no shoes, and with an empty bladder. The same scale should be used throughout the study.

The use of calibrated balance scales is recommended. Self-reported weights are not acceptable; patients must not read the scales themselves.

Height should be measured at screening; self-reported heights are not acceptable.

7.4.4. Reactogenicity Assessments

This will include an assessment of solicited events occurring from the time of each study vaccination through 7 days after the study vaccination (inclusive of vaccination day), which includes an assessment of systemic reactions (Fever; Decreased blood pressure and/or dizziness; Chills and/or sweating; Joint and/or muscle pain; Headache; Nasal congestion, runny nose, phlegm production, rhinitis; Problems with breathing (difficulty breathing, wheezing); General malaise, fatigue, loss of appetite; Itching on body/ pruritus; Swelling/ tender lymph nodes; Irritability; Rash; Cough; Sore throat; Stomach problems (abdominal pain, diarrhea, nausea, vomiting)) and local – injection site reactions (Blue spot/ bruising; Induration / Swelling; Redness / Warmth; Itching), Pain/ tenderness.

7.4.5. Medical History

Will be obtained by interview of the subjects. Subjects will be queried regarding a history of significant – clinically or from the study protocol perspective - medical disorders of the head, eyes,

ears, nose, throat, mouth, cardiovascular system, lungs, gastrointestinal tract, liver, pancreas, kidney, nervous system, blood, lymph glands, endocrine system, musculoskeletal system, skin, and genital/reproductive tract. A history of any allergies, cancer, immunodeficiency, psychiatric illness, and substance abuse will be solicited. The collection of medical history information will include a review of vaccine history and plans for vaccinations. Other vaccines history should include at least 30 days before the study and any other study-relevant vaccination received in the past.

7.4.6. Memory Aids

All subjects will complete a subject memory aid (paper diary) from the time of each study vaccination after the study vaccination. Subject memory aids will be reviewed with the subject for AEs at the site visit following the first study injection, and over the phone (unless the subject comes to the site for scheduled or unscheduled visit). If a subject noted ongoing injection site or systemic reactogenicity on the 21/28 day following the study injection day, the memory aid will continue to be completed and reviewed until resolved. Subjects will be requested to deliver memory aids filled in after the second vaccination when completed to the site.

7.4.7. Laboratory Testing

All laboratory samples (including Antibody and research samples) will be collected after assessments are performed and before a vaccine is administered at visits that correspond with a dosing day.

Samples for laboratory testing will be collected at time points according to Table 4. Schedule of Events and analyzed by a central and/or local laboratory during the study. Detailed instructions for blood sample collection are in the laboratory manual provided to study sites.

Collect the urines of all women at child-bearing age for pregnancy test, the testing results will be used for enrollment screening. Collect the nasopharyngeal swabs of all the volunteers for RT-PCR testing at the same time of the recruitment, the testing results will be used for subsequent analysis.

Pre-immunization blood collection Day 0

After enrollment, about 12.5ml of venous blood will be collected from all subject before the first dose of vaccine, the serum will be separated within 24 hours and divided into minimum of multiple tubes (each tube was not less than 0.5ml), and stored at -20 °C and below for antibody testing.

Blood collection from the subjects (all suspected or confirmed cases)

After the subjects developed typical COVID-19 symptoms, 12.5 ml venous blood will be collected for antibody testing, serum will be separated within 1-3 days and divided into multiple tubes (each tube was not less than 0.5 ml). Serum is stored at -20°C and below (subjects of confirmed cases and suspected cases are tested for antibodies).

Sample collection after immunization

After enrollment, about 12.5ml venous blood of all the subjects will be collected 14 days after the 2nd dose of immunization. Serum is separated within 24 hours and divided into multiple tubes (each

tube is not less than 0.5 ml), and stored at -20°C and below for immunogenicity antibody testing. The serums from all subjects 14 days after the 2nd dose of immunization will be matched to the serums from the monitored cases for testing of the exploratory immunological protective endpoint. Otherwise, blood samples of 900 or more subjects at each site where allocated sample size is greater than 900 are collected 28 days, 3rd month, 6th month, 9th month, 12th month after 2 doses of immunization, serum is separated within 24 hours and divided into multiple tubes (each tube is not less than 0.5 ml), and stored at -20°C and below for immunogenicity antibody testing.

Testing items for moderate, severe and critical symptomatic cases:

1. SARS-CoV-2 PCR swabs
2. Complete blood count and differential (WBC, lymphocytes...)
3. Blood chemistry (Liver function including liver enzymes, Renal function, Electrolytes, LDH, CRP, Ferritin, Glucose)
4. Coagulation profile (D-dimer)
5. Cellular immunity, cell count: CD3+, CD4+, CD8+, NK (CD56+), B (CD19+)
6. Cytokines: IL-1 β , IL-2, IL-4, IL-6, IL-8, IL-10, IL-12p70, IFN- γ , TNF- α , Th-1, Th-2, etc.
7. IgM, IgG, neutralizing antibody in acute and convalescent phase (3-4 weeks after confirmed diagnosis)
8. Chest CT scan

For trial sites where conditions permit, etiological testing for the other respiratory pathogens are required for the symptomatic cases. Items marked “*” will be also subject to site conditions.

Blood Sample Numbering Rules

Before the first dose immunization: Study No. -0

14 days after 2 doses of immunization (D35+10 days): Study No. -1

28 days after full course immunization (D49+10 days): Study No. -2

3 months after full course immunization (D111+20 days): Study No. -3

6 months after full course immunization (D201+20 days): Study No. -4

9 months after full course immunization (D291+20 days): Study No. -5

12 months after full course immunization (D381+20 days): Study No. -6

Suspected or confirmed cases: Study No. -P1, P2, P3.....

